9.2.3 Common Variable Derivations

Variable	Data Type	Definition/Calculation
Change from Baseline	All	Post-dose Observation minus Baseline Observation
Analysis Relative Day (Prior to Dose)	All	Date of Measurement minus Dose Date. In case of Part B and C it will be Date of Measurement minus Dose Date in a given treatment period.
Analysis Relative Day (Post-Dose)	All	Date of Measurement minus Dose Date +1. In case of Part B and C it will be Date of Measurement minus Dose Date in a given treatment period +1.

9.2.4 QC

The analysis datasets and the TFLs will be QC'd according to the general PRA EDS QC plan.

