9.4.3 Hypothesis Testing

No formal hypothesis testing will be done.

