10.3 Full Analysis Set

The FAS (Full Analysis Set) will consist of all subjects included in the safety set for whom at least 1 post-infusion PD assessment was completed.

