16.2.2 Pharmacokinetic Parameters

PK parameters for M254 and total IgG changes from baseline will be estimated using non-compartmental methods.

The serum PK parameters will be estimated from the concentration-time profiles. In estimating the PK parameters for the M254, BQL values at the beginning of the profile will be set to zero. BQL values that occur after the first quantifiable point will be considered missing. Values that are embedded between BQLs, or quantifiable values occurring after two or more BQLs, will be set to missing at the discretion of the pharmacokineticist. In estimating the PK parameters for the total IgG negative change from baseline values will be included in the calculation of AUC. Actual sampling times, rather than scheduled sampling times, will be used in all computations involving sampling times. If the actual time or dose time is missing, the scheduled time may be substituted in order to calculate the PK parameter.

Continuous descriptive statistics (as defined in Section 9.1.3) will be used to summarize the calculated PK parameters by study part and treatment. For t_{max} , only median, min and max will be presented. If the total number of subjects per treatment is lower than 3 then the only descriptive statistics presented will be arithmetic mean, median, minimum and maximum

The points to be included in the k_{el} range will be determined by the pharmacokineticist after inspection of the semi-log concentration-time profiles. At least 3 points will be required to be used. The C_{max} data point will not be included.

Parameters based on adjusted r² below 0.80 or %AUC_{extra} above 20% will be flagged but not excluded from descriptive statistics.

Additionally, plots of dose normalized Cmax, AUC0-inf (individual values and geometric mean) versus dose level will be provided to evaluate dose proportionality.

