17.1.2 Platelet Parameters

A therapeutic platelet count is defined as $\geq 50 \times 10^9$ /L and an increase from baseline of $\geq 20 \times 10^9$ /L (this will be referred to as threshold in Table 2: PD Parameters).

• Platelet parameters as defined in Table 2: PD Parameters

Table 2: Platelet PD Parameters calculated in WinNonLin.

Parameter	Description	Absolute values	Changes from baseline	% changes from baseline	SAS Programming Notes
t _{onset}	Time to onset of a therapeutic platelet count. Time that the response first crosses the threshold coming from the direction of the baseline value.	x			Tonset from WNL
R _{max}	Maximum platelet count following dosing, maximum and percentage platelet count change from baseline. Maximum observed response value.	x	x	x	Rmax from WNL
t _{max}	Time to maximum platelet count following dosing. Time of maximum observed response value.	X			Tmax from WNL
D _{aboveT}	Duration of a therapeutic platelet count. Total time that Response >= Threshold.	x			Time_Above_T from WNL
t _{offset}	Time greater than T _{onset} at which the curve first crosses back to the baseline side of threshold.	x			Toffset from WNL

AUC _{0-14d}	Area under the change from baseline platelet count-time curve for 14 days.	x	AUC0-14 from WNL
AUC _{0-28d}	Area under the change from baseline platelet count-time curve for 28 days.	X	AUC0-28 from WNL

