17.2.2 Platelet Parameters

Missing values in the calculation of any PD parameters will not be imputed and handled as missing values. The PD parameters for all subjects in the FAS set will be estimated from the platelet count-time profiles and platelet count change from baseline-time profiles (as specified in Table 2: PD Parameters). The calculation will be performed using the actual sampling times. If the actual time is missing, the scheduled time will be substituted in order to calculate the PD parameter.

Baseline is defined as the pre-dose sample of each period.

In calculation of AUC, the linear trapezoidal calculation method will be used. Descriptive statistics will be calculated and presented for all derived PD parameters by study part and treatment. In case of Part D by these data will be presented by planned and actual treatment (if the actual number of doses received differs from planned).

Individual PD parameters will be listed, and descriptive statistics will be summarized in tables.

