17.2.2.1 Primary Statistical Analysis of Platelet Parameters

Efficacy analyses will be performed on Part C data using FAS. This is considered primary analysis. The ratio of effects between M254 and IVIg will be estimated from a linear mixed effect model on the natural

logarithms of absolute values R_{max} and change from baseline R_{max} , AUC₀₋₁₄ and AUC₀₋₂₈, with factors for baseline platelet count, sequence, subject nested within sequence, period and treatment. The factor of subject nested within sequence will be random effect and others are fixed effects. The estimated ratio will be obtained by exponentiation of the difference of least squares means in natural log-transformed parameters between M254 and IVIg. The ratios of geometric means and their 95% CIs will be presented. The same analysis will be performed for patients with baseline platelet level of $\leq 30 \text{ vs} \geq 30 \times 10^9/\text{ L}$ as exploratory analysis and only if there is sufficient number of patients in both groups. Otherwise the platelet baseline category and category covariate interaction term will be added to the model (as exploratory analysis).

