Table 14. 2 .2.1 .1	Individual Values and Descriptive Statistics of Platelet Counts – Part B, C, D	FAS/PP
Table 14. 2.2.1.2	Individual Values and Descriptive Statistics of Platelet PD Parameters – Part B, C, D	FAS/PP
Table 14. 2.2.1 .3	Primary Statistical Platelet PD Parameters Analysis: Efficacy Analysis of M254 vs IVIg PD Parameters Ratios – Part C	FAS
Table 14. 2 .2.1 .4	Frequency counts of the responders and non responders	FAS/PP
Table 14. 2.2.1 .5	Secondary Statistical Platelet PD Parameters Analysis: Overall Platelet Response Rate – Part B, C, D	FAS/PP
Figure 14. 2.2.1 .6	Arithmetic Mean Platelet Counts Absolute Values versus Time Profile (Linear and Semi-logarithmic) - Part B, C, D	FAS/PP
Figure 14. 2.2.1 .7	Arithmetic Mean Platelet Counts Changes from Baseline versus Time Profile (Linear and Semi- logarithmic) - Part B, C, D	FAS/PP
Figure 14. 2.2.1 .8	Arithmetic Mean Platelet Counts % Changes from Baseline versus Time Profile (Linear and Semi- logarithmic) - Part B, C, D	FAS/PP
Figure 14. 2.2.1 .9	Combined Individual Platelet Counts Absolute Values versus Time Profile (Linear and Semi-logarithmic) – Part B, C, D	FAS
Figure 14. 2.2.1.10	Combined Individual Platelet Counts Changes from Baseline versus Time Profile (Linear and Semi- logarithmic) – Part B, C, D	FAS
Figure 14. 2.2.1 .11	Combined Individual Platelet Counts % Changes from Baseline versus Time Profile (Linear and Semi- logarithmic) – Part B, C, D	FAS
Figure 14. 2.2.1 .12	Individual Platelet Counts Absolute Values versus Time Profile (Linear and Semi-logarithmic) - Part B, C, D	FAS

Figure 14. 2.2.1 .13	Individual Platelet Counts Changes from Baseline versus Time Profile (Linear and Semi-logarithmic) - Part B, C, D	FAS	
Figure 14. 2.2.1 .14	Individual Platelet Counts % Changes from Baseline versus Time Profile (Linear and Semi-logarithmic) - Part B, C, D	FAS	
Section 14.3 – Saf	ety Data		
14.3.1 Adverse Ev	rents		
Table 14.3.1.1	Overview TEAE	Safety	Y ¹
Table 14.3.1.2	Summary of Treatment-Emergent Adverse Events by System Organ Class and Preferred Term – Part A, B, C, D	Safety	Y ¹
Table 14.3.1.3	Summary of Related Treatment-Emergent Adverse Events by System Organ Class and Preferred Term – Part A, B, C, D	Safety	Y ¹
Table 14.3.1.4	Summary of Serious Adverse Events by System Organ Class and Preferred Term – Part A, B, C, D	Safety	Y ¹

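### Two of the four primary Part C platelet models take logs of AUCs that can be zero or negative, so the AUC0-14 and AUC0-28 ratios describe positive-AUC periods only

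*SAP*

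**What the plan says.** SAP 17.2.2.1 names the Part C efficacy analysis in the Full Analysis Set as primary. It fits linear mixed models to the natural logs of four parameters: absolute Rmax, change-from-baseline Rmax, AUC0-14 and AUC0-28. The fixed effects are baseline count, sequence, period and treatment; subject within sequence is random. The effect is a ratio: "The estimated ratio will be obtained by exponentiation of the difference of least squares means in natural log-transformed parameters between M254 and IVIg". Protocol 9.3.1 likewise puts AUC on the log scale.

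Three other places fix the sign of the AUC:
- SAP 17.1.2, Table 2, defines AUC0-28 as "Area under the change from baseline platelet count-time curve for 28 days". AUC0-14 is the same over 14 days.
- SAP 9.2.3 defines change as "Post-dose Observation minus Baseline Observation".
- SAP 17.2.2 uses the linear trapezoidal rule with the pre-dose sample of each period as baseline. It sets no floor at zero.

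The only handling rule in SAP 17.2.2 is for missing data: "Missing values in the calculation of any PD parameters will not be imputed and handled as missing values". The Full Analysis Set is defined by subject: "all subjects included in the safety set for whom at least 1 post-infusion PD assessment was completed". The results go to Table 14.2.2.1.3, "Efficacy Analysis of M254 vs IVIg PD Parameters Ratios", with the population given as FAS.

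**The concern.** A period in which the count spends enough time below its pre-dose value has a negative AUC. That AUC is observed, but it cannot enter a log-scale model. The Statistical Methods document, section 2, states that the SAP had no provision for negative AUCs and that they were left out; section 3 repeats this.

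The exclusion depends on the outcome. The periods removed are those with poor platelet profiles, and the model's confidence interval takes no account of their removal. A reader of Table 14.2.2.1.3, which is labelled FAS, would take the two AUC ratios as covering every observed period. An affected patient's other period still contributes through the random subject effect, but that patient's own M254-versus-IVIg contrast on that AUC is lost.

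Change-from-baseline Rmax has the same exposure in principle, because it is at or below zero if no post-dose count exceeds baseline.

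**Working it through.** **1. Can the AUC be negative while Rmax is fine?** Take an invented patient on the Part C sampling days. Counts (10^9/L) are 40 pre-dose, 42 at 4 h, then 48, 55, 52, 46, 38, 36, 35, 34, 33, 32, 32 on Days 2, 3, 4, 5, 8, 10, 12, 15, 18, 22, 29. The largest change is 55 − 40 = +15, so both Rmax models keep the period. Trapezoids of the change, in 10^9/L × days:
- to 14 days: 0.17 + 4.17 + 11.5 + 13.5 + 9 + 6 − 6 − 9 − 16.5 = 12.83, and × 24 gives AUC0-14 = +308
- from 14 to 28 days: −19.5 − 30 − 56 = −105.5
- total: −92.67, and × 24 gives AUC0-28 = −2224 (10^9/L × h)

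This period enters three models and drops out of AUC0-28.

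**2. Reproducing the printed intervals** (Statistical Methods 4.1, all subjects). Interval = estimate ± t(0.975, df) × SE; ratio = exp(estimate).
- AUC0-14: −1.4084 ± 2.306 × 0.4696 gives −2.4913 to −0.3255 (printed −2.4914 to −0.3255).
- AUC0-28: −1.5289 ± 2.379 × 0.4149 gives −2.5159 to −0.5419 (printed −2.5158 to −0.5419).

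The two Rmax intervals reproduce equally closely.

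| Parameter | Used / read | Unused | Ratio M254/IVIg (95% CI) |
|---|---|---|---|
| Rmax | 21/21 | 0 | 0.494 (0.379–0.643) |
| Change-from-baseline Rmax | 21/21 | 0 | 0.273 (0.172–0.434) |
| AUC0-14 | 19/21 | 2 (2/21 = 9.5%) | 0.245 (0.083–0.722) |
| AUC0-28 | 17/21 | 4 (4/21 = 19.0%) | 0.217 (0.081–0.582) |

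With at most two periods per patient, 21 observations allow at most 10 complete pairs; 19 and 17 allow at most 9 and 8.

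**3. Would a small positive substitute rescue the log model?** This is an illustration, not an estimate of bias. Assume 11 M254 and 10 IVIg periods, both unused AUC0-14 values non-positive, each replaced by a value v, and arm means recalculated from the printed least squares means (M254 7.9716, IVIg 9.3800).
- Both in M254, v = 1: (9 × 7.9716 + 2 × 0)/11 − 9.3800 = −2.858, ratio 0.06.
- Both in IVIg, v = 1: 7.9716 − (8 × 9.3800 + 2 × 0)/10 = 0.468, ratio 1.60.
- With v = 1000 (log 6.908), the same two cases give 0.20 and 0.40.

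The answer depends on an arbitrary constant and on the unknown arm. A scale that accepts signed values is needed. No corrected AUC result can be computed, because the excluded values are not in the documents.

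**The case against.** The strongest reply is that the plan already reports the negative AUCs. SAP 17.2.2 calls for descriptive statistics on all derived platelet parameters and a listing of individual values. Table 14.2.2.1.2 carries both for the FAS. The Part B and C layout in SAP 9.5 has a column for the difference between the M254 and IVIg periods. The arithmetic mean, median and range accept any sign. The response rates in SAP 17.2.2.2 need no logarithm, and both Rmax models are complete. In addition, SAP 3.0 lets changes of analysis be reported in the CSR without a SAP update, and the exclusion is listed as a deviation. Part C is exploratory (Protocol 9.1), and SAP 9.4.3 states: "No formal hypothesis testing will be done".

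All of that stands. It narrows the gap to a model-based estimate and interval covering every observed period, together with a count of what was left out and where. It does not make the two ratios full-FAS estimates.

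Two stronger readings should be resisted. A reader might infer that the SAP solved this problem for total IgG and overlooked it for platelets, since SAP 16.2.2 says: "In estimating the PK parameters for the total IgG negative change from baseline values will be included in the calculation of AUC". That sentence concerns integrating negative concentration changes. It is not a rule for a non-positive AUC in a log model, and no such model is planned for IgG. A reader might also subtract the output for baseline ≤30 (11/11 and 10/11 used) from the all-subject output and infer that losses concentrate at higher baselines. Those counts are very small and may mix negative, zero and missing values, so they support no such conclusion.

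**Conclusion.** The point holds. As specified, two of the four primary Part C models cannot use every observed FAS period, and the appended document confirms that negative AUCs were excluded. The ratios 0.245 and 0.217 are correctly calculated but apply to periods with AUC above zero.

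The size is bounded, not known. At most 2 of 21 and 4 of 21 observations were lost for this reason. A reader might take all of them as negative AUCs, but the output does not separate negative, zero and missing values.

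The direction is also unknown. Retained M254 periods correspond to an average rise of only exp(7.9716)/336 = 8.6 × 10^9/L over 14 days, against exp(9.3800)/336 = 35.3 for IVIg. A reader might infer from this that the lost periods were mostly M254 and that the exclusion flatters it. The supplied output does not give the arm of any unused observation, so that inference is unsupported. The individual listing should settle it.

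Change-from-baseline Rmax shares the weakness in principle but lost nothing. Rating: should-fix, at the lowest level, because Part C is exploratory and without formal testing, and the exclusion is disclosed.

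**What to change.** Keep the specified log-ratio models and make three additions.

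1. Label the AUC0-14 and AUC0-28 ratios as *periods with AUC > 0 only* in Table 14.2.2.1.3 and in the CSR text.
2. Tabulate the unused observations for each AUC by arm, period and reason (negative, zero, missing).
3. Beside each ratio, report the M254 minus IVIg difference in untransformed AUC with its 95% CI. Use the same mixed model (baseline, sequence, period, treatment, random subject within sequence) on all observed FAS periods, and mark it post hoc. Do the same for change-from-baseline Rmax if any value is at or below zero.

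The cost is a label, one table and two further models, with no new data. The added effect is a difference, so it cannot be compared directly with the protocol's ratio. Its t-based interval will be imprecise and sensitive to skew with about ten patients. Missing AUCs stay missing. If only one item can be done, the table should come first, because it shows which arm lost periods and why.

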17.2.2.2 Secondary Statistical Analysis of Platelet Parameters

For Part C the frequency counts of the responders and non-responders will be provided, according to the Table 3.

Parameter	Description	SAS Programming Notes
Patients with response (R) for patients with baseline ≤30 × 10 ⁹ / L	Platelet count of $\geq 30 \times 10^9$ /L and at least 2-fold increase of the baseline count, confirmed on at least 2 separate occasions at least 7 days apart and the absence of bleeding during the 28 days after dose.	Count and count of patients with baseline ≤30× 10 ⁹ / L
Patients with complete response (CR) for patients with baseline ≤30 × 10 ⁹ / L	Platelet count of $\geq 100 \times 10^{9}$ / L and at least 2-fold increase of the baseline count, confirmed on at least 2 separate occaions at least 7 days apart and the absence of bleeding during the 28 days after dose.	Count and count of patients with baseline ≤30× 10 ⁹ / L
Patients with no response (NR) for patients with baseline ≤30 × 10 ⁹ / L	Platelet count $<30 \times 10^{9}$ / L or less than 2-fold increase of baseline platelet count, confirmed on at least 2 separate occasions approximately 1 day apart, or bleeding during the 28 days after dose.	Count and count of patients with baseline ≤30× 10 ⁹ / L
Patients with loss of CR or R for patients with baseline ≤30 × 10 ⁹ / L	Platelet count below 100×10^9 / L or bleeding (from CR) or below 30×10^9 / L or less than 2-fold increase from baseline platelet count or bleeding (from R). Platelet counts confirmed on at least 2 separate occasions at least 1 day apart.	Count and count of patients with baseline ≤30× 10 ⁹ / L

Table 3: Patient PD parameters.

For Part C overall platelet response rate and its 90% exact binomial Cl in each treatment period will be presented for the FAS and PP set as secondary analysis. Overall platelet response rate is defined as reaching the therapeutic platelet count.

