#### 6.1.1.1 M254 and IVIg Infusion Rate

M254 and IVIg is administered by IV infusion at a rate of up to a maximum of CCI whichever is lower (CCI is less than infusion rates recommended for

Compound: M254 Protocol: MOM-M254-001

Protocol Date and Version:8 Global 28 April 2020

[figure not shown]
IVIg). After completion of the infusion, the IV line should be flushed with approximately 50 mL of 5% dextrose in water (D5W) within 10 minutes of completion of the infusion to ensure that the entire intended dose of drug product has been infused and none is retained in the IV tubing; other methods for ensuring accurate dosing may be used upon agreement of the Sponsor. Additional dosing information is provided in the study Infusion Manual.

The initially-planned infusion rate schedule is described in Table 6-1; the infusion rate and duration at an infusion rate may be increased or decreased as part of the dose escalation decision with the restriction that it may not be >4 mg/kg/min.

Table 6-1. M254 and IVIg Infusion Rate

Start Time (minutes relative to Infusion Start)	End Time (minutes relative to Infusion Start)	Infusion Rate (mg/kg/minute)
0	30	0.5
30	60	1
60	90	2
90	360	4

Two specific examples of implementing the above infusion rate table for the rate are:

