9.1.5 Unscheduled Measurements

Unscheduled measurements will be included in the listings. For Part A, unscheduled measurements will be excluded from the descriptive statistics and statistical analysis (with the exception of unscheduled measurements used for baseline).

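### SAP Table 3 gives non-response its own rule, so one Part C patient can count as both responder and non-responder

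*SAP*

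**What the plan says.** SAP 17.2.2.2 takes the Part C counts of responders and non-responders from Table 3, for patients with baseline at or below 30 × 10⁹/L.

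- **R:** a count of at least 30 × 10⁹/L and "at least 2-fold increase of the baseline count, confirmed on at least 2 separate occasions at least 7 days apart", with no bleeding in the 28 days after dosing. CR is the same with a threshold of 100 × 10⁹/L.
- **NR:** a count below 30 × 10⁹/L or "less than 2-fold increase of baseline platelet count, confirmed on at least 2 separate occasions approximately 1 day apart". Bleeding is a separate route into this row, worded as "or bleeding during the 28 days after dose".
- **Loss of CR or R:** a fall below the relevant level, or bleeding. Here the confirmation is worded differently: "Platelet counts confirmed on at least 2 separate occasions at least 1 day apart".

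In the NR row the 28-day window belongs to bleeding, not to the counts. The planned output is SAP Appendix 4, Table 14.2.2.1.4, "Frequency counts of the responders and non responders". SAP 9.5 says that no table shells will be provided. Section 2 of the Statistical Methods and Analysis Output, which lists deviations from the SAP and decisions made during analysis, does not mention the classification.

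**The concern.** On any single count, the platelet conditions for R and NR are complements. Over a whole treatment period they are not, because they may be met on different days and with different confirmation gaps. Low counts before onset can satisfy NR, and a later sustained rise can satisfy R or CR. Table 3 does not say that NR requires R never to have been met, and it does not rank the rows.

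What is at stake is the meaning of the non-responder row. As written it can include slower-onset responders, so it partly measures speed of onset, and its size depends on how the programmer reads the rule. Part C compares two products, and the documents give no onset times for one of them (M254).

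**Working it through.** The plan states no figure to reproduce. This is a check of the logic of Table 3 against the visit schedule.

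**Inputs.** Post-dose platelet visits in Part C (Protocol Table 1-3): 4 h after infusion on Day 1, then Days 2, 3, 4, 5, 8, 10, 12, 15, 18, 22 and 29, which is 12 visits. Rules: SAP Table 3. No bleeding is assumed; bleeding cannot create an overlap, because R requires its absence.

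**Step 1: a worked profile.** Baseline 20, so a responding count must be at least 40 (2 × 20, which exceeds 30).

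| Visit | 4 h | D2 | D3 | D4 | D5 | D8 | D10 | D12 | D15 | D18 | D22 | D29 |
|---|---|---|---|---|---|---|---|---|---|---|---|---|
| Count (10⁹/L) | 21 | 24 | 28 | 75 | 120 | 150 | 140 | 130 | 110 | 70 | 35 | 24 |

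- R: Days 4 and 12 (75 and 130), 8 days apart. Met.
- CR: Days 5 and 12 (120 and 130), 7 days apart. Met.
- NR: Days 2 and 3 (24 and 28, both below 30), 1 day apart. Met.

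With Day 2 changed to 45 and Day 3 to 75, the profile still meets R and CR but not NR at any spacing up to 2 days. The double classification turns on early onset alone.

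**Step 2: the 4 h/Day 2 pair.** Whether these two counts are about 1 day apart depends on where Day 2, hour 0 is timed from, which Protocol Table 1-3 does not say.

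- Timed from the end of infusion: 24 − 4 = 20 h (0.83 day).
- Timed from the start: Protocol 6.1.1.1 states that "The initially-planned infusion rate schedule is described in Table 6-1". The first 90 minutes deliver 30 × 0.5 + 30 × 1 + 30 × 2 = 105 mg/kg. At 1000 mg/kg the rest takes (1000 − 105)/4 = 223.75 min, so the infusion lasts 313.75 min = 5.23 h and the gap is 24 − 5.23 − 4 = 14.8 h (0.62 day).

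Both readings, pair accepted and pair excluded, are carried below.

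**Step 3: enumeration.** Take every pattern with one unbroken run of responding counts: 12 × 13 / 2 = 78. R is met if two responding counts are at least 7 days apart. The 4 h to Day 8 interval falls short: 168 − 4 = 164 h when timed from the end of infusion. R is met by 41 patterns.

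| First responding visit | R patterns | Also NR, 24-h pairs only | Also NR, 4 h/Day 2 pair accepted |
|---|---|---|---|
| 4 h or Day 2 | 12 | 0 | 0 |
| Day 3 | 6 | 0 | 6 |
| Day 4 or 5 | 10 | 10 | 10 |
| Day 8 or later | 13 | 13 | 13 |
| Total | 41 | 23 | 29 |

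Allowing spacings up to 2 days leaves the overlap at 23 (pair excluded) or 29 (pair accepted).

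**Step 4: the opposite gap.** On a strict 24-h reading, runs that start at 4 h, Day 2 or Day 3 and end on Day 4, 5 or 8 meet neither R nor NR: 3 × 3 = 9 of 78. Accepting the 4 h/Day 2 pair removes the three that start on Day 3, leaving 6. At spacings up to 2 days the gap is 0.

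**Limits.** Only nominal visits were used. SAP 17.2.2 uses actual sampling times, and SAP 9.1.5 restricts the exclusion of unscheduled counts to one part: "For Part A, unscheduled measurements will be excluded from the descriptive statistics and statistical analysis". Real Part C data could therefore hold further qualifying pairs of low counts.

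**The case against.** The strongest reply is that the ordinary reading gives one answer. The row is titled as patients with no response, and a separate row deals with loss of response, so NR must mean a patient who never responded. That is very likely the intent. But no section states it, Table 3 is the programming specification, and two programmers following it could produce different counts.

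The second reply is about plausibility. Of the 23 overlaps that hold on every reading, 13 have their first responding count on Day 8 or later, and only 10 on Day 4 or 5. Protocol 2.2.1 says that an IVIg response is normally seen within 24 hours, and no R pattern with onset by Day 2 overlaps at spacings up to 2 days. This stands: the practical effect may be small. It does not settle the matter for M254, whose onset times are not given.

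Stronger readings are tempting but unsupported:

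- A reader might infer from 23 of 41 that more than half of responders would be misclassified. The patterns are unweighted possibilities.
- A reader might enlarge the overlap by stretching about 1 day to several days. The wording does not reasonably allow that.
- A reader might express one double-counted period as a share of the 11 observations in the baseline ≤30 model output. SAP 9.1.4 and 9.5 keep M254 and IVIg separate, and nothing says that Table 3 uses those records.
- A reader might infer that a reported count is wrong. The documents contain no reported R or NR count.

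**Conclusion.** The NR rule is wrong as written: a confirmed responder, even a complete responder, can also satisfy it. The severity is minor. The overlap is certain for any patient with low counts on Days 2 and 3 who later meets R. For onset on Day 3 it depends on how the 4 h/Day 2 pair is read. The gap, in which a short early response meets neither row, arises only on a strict 24-h reading.

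The reach is one secondary descriptive table in the baseline ≤30 subset. The R and CR rules are unaffected. So are the primary mixed model and the overall response rate with its 90% interval, which rests on the therapeutic platelet count. The pattern counts assume nominal visits, one response episode and no bleeding.

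**What to change.** For each patient and treatment period, classify in a stated order.

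1. Apply R and CR exactly as Table 3 states them, and add no new time window. Table 3 ties its 28 days to bleeding, and Day 29 has a ±3-day window. Responding counts on Days 22 and 31, for example, meet R as written, and a new 28-day limit on counts would remove them.
2. Define NR as R not met, including bleeding within 28 days, among patients with enough counts to assess R.
3. List the others as not evaluable: for example, a patient without bleeding who does not meet R but would have met it had the missing scheduled counts been responding counts. This is needed because SAP 17.2.2 says: "Missing values in the calculation of any PD parameters will not be imputed and handled as missing values".
4. Report CR as a subset of R.
5. Count loss of response only after R or CR has been met.

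The cost is SAP wording and one re-derived descriptive table. R and CR counts do not change. NR counts may move either way. In the pattern set NR becomes 78 − 41 = 37, from 51 with 24-h pairs only (51 − 23 + 9) or from 60 with the 4 h/Day 2 pair accepted (60 − 29 + 6). One consequence should be accepted openly: a rise held for less than 7 days is labelled NR. A sentence giving R precedence over NR would cure the overlap without that label, but would leave the gap on the strict reading.
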